1.3.2 Primary Endpoint

The primary endpoint is a composite rate of all death or all myocardial infarction (modified Academic Research Consortium [ARC]) from 1 month to 6 months.

1.3.3 Secondary Endpoint(s)

1.3.3.1 Major Secondary Endpoint(s)

- Major bleeding rate (BARC type 2-5) from 1 to 6 months.

1.3.3.2 Other Secondary Endpoint(s)

The following endpoints will be assessed from 1 to 6 months:

- Stent thrombosis (ARC definite/probable, ARC definite)
- All death, cardiac death, vascular death, non-cardiovascular death
- All myocardial infarction (MI) and MI attributed to target vessel (TV-MI, modified ARC)
- Composite of cardiac death or MI (modified ARC)
- Composite of all death or all MI (modified ARC)
- All stroke, ischemic stroke and hemorrhagic stroke
- Clinically-indicated target lesion revascularization (CI-TLR)
- Clinically-indicated target vessel revascularization (CI-TVR)
- Target lesion failure (TLF, composite of cardiac death, TV-MI and CI-TLR)
- Target vessel failure (TVF, composite of cardiac death, TV-MI and CI-TVR)

[figure not shown]
[figure not shown]
- Major bleeding defined by the Bleeding Academic Research Consortium (BARC) type 3-5

The primary endpoint and the major secondary endpoint, as well as all the above secondary endpoints will also be assessed from 6 months to 12 months and from 1 month to 12 months, respectively.

1.4 Analysis Populations

Primary Analysis Population

The primary analysis population includes “1-month clear” population, defined as subjects who are free from myocardial infarction (modified ARC), repeat coronary revascularization, stroke, or stent thrombosis (ARC definite/probable) within 1 month

The above defined “1-month clear” population will be pooled from the XIENCE 28 USA Study and XIENCE 28 Global Study for both the primary and major secondary endpoint analyses. In this SAP the term ‘pooled 1-month DAPT arm’ refers to subjects pooled from the XIENCE 28 USA Study and XIENCE 28 Global Study, unless otherwise specified.

1.5 Sample Size Calculations

- [REDACTED]
- Sample size:
 - Test arm: a total of ~1,600 subjects pooled from the XIENCE 28 USA Study and the XIENCE 28 Global Study
 - Historical control: ~1400 “1-month clear” subjects from the XIENCE V USA

[REDACTED]

[REDACTED]

[REDACTED]

[REDACTED]

[REDACTED]

[REDACTED]

[REDACTED]

[REDACTED]

[REDACTED]

2. ANALYSIS CONSIDERATIONS

2.1 Statistical Methods

Baseline demographic, clinical, angiographic, procedural, and device data, and clinical results will be summarized using descriptive summary statistics.

2.1.1 Descriptive Statistics for Continuous Variables

For continuous variables (e.g., age, percent diameter stenosis and lesion length), results will be summarized with the numbers of observations, means, and standard deviations and where specified in the table mockups, with quartiles, minimums, maximums, and two-sided 95% confidence intervals for the means as per the table mockups. Differences between two comparison groups of interest, where specified, will be summarized with the differences of the two means, and two-sided 95% confidence intervals for the difference between the means. These calculations will be done under the assumption that the data for the two arms are independent and approximately normal in distribution. The confidence interval for the difference of two means will be calculated under the assumption of unequal variances. If the asymptotic assumptions fail, then nonparametric summary statistics (medians, 25th and 75th percentiles) may be displayed as an alternative.

Formulas for calculation of the confidence intervals for the continuous variables are given below:

1. 100(1- α)% Confidence Interval For A Single Mean⁵

$$\bar{x} \pm t_{\frac{\alpha}{2}} \frac{s}{\sqrt{n}}$$

where:

\bar{x} = sample mean

s = sample standard deviation

n = sample size

$t_{\frac{\alpha}{2}}$ = the alpha/2 t - statistic for $n - 1$ degrees of freedom

2. 100(1- α)% Confidence Interval For The Difference of Two Means Under The Assumption Of Equal Variances Between The Two Groups⁵

$$(\bar{x}_1 - \bar{x}_2) \pm t_{\frac{\alpha}{2}} \sqrt{s_p^2 \left(\frac{1}{n_1} + \frac{1}{n_2} \right)}$$

where:

\bar{x}_1 = sample mean for group 1

\bar{x}_2 = sample mean for group 2

$$s_p^2 = \frac{(n_1 - 1)s_1^2 + (n_2 - 1)s_2^2}{n_1 + n_2 - 2}$$

s_1 = sample standard deviation for group 1

s_2 = sample standard deviation for group 2

n_1 = sample size for group 1

n_2 = sample size for group 2

$t_{\frac{\alpha}{2}}$ = the alpha/2 t - statistic for $n_1 + n_2 - 2$ degrees of freedom

3. 100(1- α) % Confidence Interval for the Difference of Two Means under the Assumption of Unequal Variances between the Two Groups⁵

$$(\bar{x}_1 - \bar{x}_2) \pm t_{\frac{\alpha}{2}} SED$$

With the degrees of freedom for the approximate t statistic is determined by Satterthwaite's formula² as follows:

$$df = \frac{(w_1 + w_2)^2}{\frac{w_1^2}{n_1 - 1} + \frac{w_2^2}{n_2 - 1}}$$

where:

\bar{x}_1 = sample mean for group 1

\bar{x}_2 = sample mean for group 2

s_1 = sample standard deviation for group 1

s_2 = sample standard deviation for group 2

n_1 = sample size for group 1

n_2 = sample size for group 2

$$SED = \sqrt{\frac{s_1^2}{n_1} + \frac{s_2^2}{n_2}}$$

$$w_1 = \frac{s_1^2}{n_1}$$

$$w_2 = \frac{s_2^2}{n_2}$$

2.1.2 Descriptive Statistics for Categorical Variables

For categorical variables such as gender, Death/MI and TLF, results will be summarized with subject counts and percentages/rates, [REDACTED] with exact two-sided 95% Clopper-Pearson⁶ confidence intervals. Differences between two comparison groups of interest, when specified, will be summarized with the difference in percentages and the Newcombe⁵ score two-sided 95% confidence interval for the difference of two percentages.

For efficacy and safety endpoint(s), relative risks (i.e., the ratio of rates), confidence interval for the relative risks, the difference in rates and the confidence interval for difference in rates (using previously-described formulas), and p-values may also be presented for hypothesis generating purposes. The p-values will be based on either Pearson's Chi-square test or Fisher's exact test by checking the expected frequency for each cell in the 2x2 contingency table against Cochran's rule⁸, i.e., if the expected frequencies for all cells are ≥ 5 , then Pearson's Chi-square test will be used, otherwise Fisher's exact test will be used.

[REDACTED]

[REDACTED]

[REDACTED]

[REDACTED]

Formulas for calculating confidence intervals for the categorical variables are given below.

1. 100(1- α) % Exact Clopper-Pearson Confidence Interval for A Single Proportion⁶

$$\text{Lower Confidence Limit} = \frac{x}{x + (n - x + 1)F_{\frac{1-\alpha}{2}}(2(n - x + 1), 2x)}$$

$$\text{Upper Confidence Limit} = \frac{(x+1)F_{1-\frac{\alpha}{2}}(2(x+1), 2(n-x))}{n - x + (x+1)F_{1-\frac{\alpha}{2}}(2(x+1), 2(n-x))}$$

where:

n = sample size

x = number of "events"

$F_{1-\frac{\alpha}{2}}(df_1, df_2)$ = the $(1 - \alpha/2)$ F - statistic for degrees of freedom df_1 and df_2

2. 100(1- α) % Newcombe Score Confidence Interval for the Difference of Two Proportions ⁷

a. 100(1- α) % Wilson Score Confidence Interval for A Single Proportion⁵

$$\text{Lower Confidence Limit} = \left(\hat{p} + Z_{\alpha/2}^2 / 2n - Z_{\alpha/2} \sqrt{(\hat{p}(1-\hat{p}) + Z_{\alpha/2}^2 / 4n) / n} \right) / \left(1 + Z_{\alpha/2}^2 / n \right)$$

$$\text{Upper Confidence Limit} = \left(\hat{p} + Z_{\alpha/2}^2 / 2n + Z_{\alpha/2} \sqrt{(\hat{p}(1-\hat{p}) + Z_{\alpha/2}^2 / 4n) / n} \right) / \left(1 + Z_{\alpha/2}^2 / n \right)$$

where:

$\hat{p} = x / n$

n = sample size

x = number of "events"

$Z_{\alpha/2}$ = 100(1- $\alpha/2$)th percentile of the standard normal distribution

b. 100(1- α) % Newcombe Score Confidence Interval for the Difference of Two Proportions⁴

$$\text{Lower Confidence Limit} = (\hat{p}_1 - \hat{p}_2) - Z_{\alpha/2} \sqrt{L_1(1-L_1)/n_1 + U_2(1-U_2)/n_2}$$

$$\text{Upper Confidence Limit} = (\hat{p}_1 - \hat{p}_2) + Z_{\alpha/2} \sqrt{U_1(1-U_1)/n_1 + L_2(1-L_2)/n_2}$$

where:

\hat{p}_1 = sample proportion for group 1

\hat{p}_2 = sample proportion for group 2

L_1 and U_1 are the lower and upper Wilson Score confidence limits for p_1

L_2 and U_2 are the lower and upper Wilson Score confidence limits for p_2

$Z_{\alpha/2}$ = 100(1 - $\alpha/2$)th percentile of the standard normal distribution

2.1.3 Propensity Score

Given that subjects in the two comparison groups (pooled 1-month DAPT arm vs XIENCE V USA historical control) are not randomized and thus may not have balanced baseline characteristics, the non-inferiority and superiority tests for 1-6 month period will be carried out through stratified analysis in the “1-month clear” population. The stratification will be performed through propensity scores (PS). For each individual a propensity score (i.e., predicted probability between 0 and 1) for group (pooled 1-month DAPT arm) membership will be calculated using logistics regression, with “group” as the outcome and baseline variables including demographic, lesion characteristics, and risk factors as the predictors. Subjects will be categorized into 5 groups based on the calculated propensity scores and their quintiles. Non-inferiority and superiority will then be carried out for the rate of the endpoint using the method described in sections below stratified by the propensity quintiles.

The propensity score modeling and design will be performed by an independent statistician who has no access to any outcome data of the XIENCE 28 USA study, XIENCE 28 Global study and the XIENCE V USA historical control for the integrity and interpretability of study results. The independent statistician will be blinded and have no access to clinical outcome and any follow-up information to avoid introducing bias into the analysis.

Per the recent publication by Yue et al²⁸ on two-stage study designs involving propensity score adjustment, the propensity score calculation results will subsequently be sent to the FDA for review and approval prior to performing the primary endpoint and major secondary endpoint analyses.

2.1.3-1 Propensity Score Variable List

Based on prior clinical experience and clinical research, below is the list of variables that are considered to be related to assignments modeling building:

- Gender
- Age
- Creatinine
- Chronic anticoagulant
- History of stroke
- History of major bleeding
- Platelet
- Hb
- BMI

- Hypertension
- Dyslipidemia
- Prior PCI
- Prior CABG
- Prior MI
- Multivessel disease
- Clinical presentation (ACS (NSTEMI, ACS unstable angina) vs. non-ACS)
- Diabetes
- ACC/AHA lesion complexity
- Total lesion length per patient
- RVD
- Diameter stenosis%
- Bifurcation
- Number of lesions treated
- Number of vessel treated
- Number of stents per patient
- Total stent length per patient
- Discharge P2Y12
- Paris bleeding score
- PRECISE DAPT score

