6.1.2 Clinical Assessments

Subject demographics (age, gender, race), height, weight, family history of coronary artery disease (CAD), smoking status, cardiac history (myocardial infarction, diabetes mellitus, hypertension, hypercholesterolemia, and previous PCI/CABG information), subject's current cardiac status (presentation of CAD and multivessel disease) and indication of high bleeding risk (per criteria specified in **Section 5.3.1.1**) will be obtained and recorded in electronic case report form (eCRF).

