2.7 Adjustments for Covariates

Unless otherwise specified, no adjustments for covariates will be made for any of the variables in the analyses.

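### Smoking status is recorded at baseline in XIENCE 28 USA but is not a covariate in its own right in the propensity score, and no other visible analysis adjusts for it

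*SAP*

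**What the plan says.** Protocol 6.1.2 lists the baseline data entered in the eCRF, including "height, weight, family history of coronary artery disease (CAD), smoking status, cardiac history". The cardiac history items are MI, diabetes, hypertension, hypercholesterolemia and previous PCI or CABG.

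SAP 2.1.3 explains why adjustment is needed: the two groups "are not randomized and thus may not have balanced baseline characteristics". It describes the model inputs as "baseline variables including demographic, lesion characteristics, and risk factors as the predictors". List 2.1.3-1, introduced by "below is the list of variables that are considered to be related to assignments modeling building", has 29 entries. They include hypertension, dyslipidemia, diabetes, BMI, prior MI, prior PCI and prior CABG, and two composites, the "Paris bleeding score" and the "PRECISE DAPT score". Smoking is not listed, and no reason is given.

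SAP 2.7 states that, unless otherwise specified, "no adjustments for covariates will be made for any of the variables in the analyses". SAP 2.1.3 also assigns the propensity modelling to an independent statistician with no access to outcomes, and sends the results to the FDA for approval before the endpoint analyses.

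**The concern.** There is no randomized control, so the covariate list carries the whole burden of making the groups comparable. The control is a completed US post-approval study (SAP 1.3). The test arm is newer and pools 640 to 800 US and Canadian subjects with at least 800 from outside the US. Era and region could both bring a difference in smoking.

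The list takes up the variables recorded next to smoking in Protocol 6.1.2 but not smoking itself, although the SAP says that risk factors are among the predictors. If smoking is related to death/MI and its frequency differs between the groups within propensity quintiles, the stratified non-inferiority test compares unlike groups on a variable that could have been balanced. If the test arm has fewer smokers, the test is more likely than its nominal level to declare non-inferiority wrongly.

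**Working it through.** **1. Is smoking adjusted for anywhere?**

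| Place | Finding |
|---|---|
| Protocol 6.1.2 | Smoking status recorded |
| SAP 2.1.3-1 | 29 covariates; smoking not named |
| SAP 2.2.1 | Quartile sensitivity analysis: same method, different number of strata |
| SAP 2.3 | Subgroups do not include smoking |
| SAP 2.7 | No other covariate adjustment unless specified |
| SAP 2.9 | Covers compliance, a comparison with XIENCE 90, and missing outcomes |

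The only possible route is indirect, through the two composite scores or through correlation with listed covariates.

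**2. Inputs for an illustration.** The plan gives no figure to reproduce here: the expected rates and the margin are not visible in SAP 1.5.

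- From the documents: about 1,600 test subjects and about 1,400 controls (SAP 1.5); significance level 0.025 (Protocol 9.4), taken here as one-sided.
- Assumed: 1- to 6-month death/MI R = 4%; 15% smokers overall; relative risk RR for smokers 1.5 to 2.0; difference in smoking prevalence d = 10 points; no indirect adjustment through other covariates.

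**3. Bias in the risk difference.** The risk in non-smokers is r0 = R / (1 + 0.15 × (RR − 1)), and the bias is d × r0 × (RR − 1).

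- RR 1.5: r0 = 0.04 / 1.075 = 0.0372; bias = 0.10 × 0.0372 × 0.5 = 0.0019, or 0.19 points.
- RR 2.0: r0 = 0.04 / 1.15 = 0.0348; bias = 0.10 × 0.0348 × 1.0 = 0.0035, or 0.35 points.
- Wider range: 5 points with RR 1.5 gives 0.09 points; 15 points with RR 2.0 gives 0.52 points.

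**4. Standard error, unstratified.** SE = sqrt(0.04 × 0.96 × (1/1600 + 1/1400)) = 0.0072, or 0.72 points. The bias in the 10-point case is therefore 0.19/0.72 = 0.26 to 0.35/0.72 = 0.49 of a standard error.

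**5. Error rate at the non-inferiority boundary.**

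- Fewer smokers in the test arm: 1 − Φ(1.96 − bias/SE), about 0.045 (RR 1.5) to 0.070 (RR 2.0) instead of 0.025.
- More smokers in the test arm: 1 − Φ(1.96 + bias/SE), about 0.013 to 0.007, which is conservative.

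**6. Other assumptions.** With death/MI 3% to 8%, RR 1.3 to 2.0 and d from 3 to 10 points, the bias runs from 0.03 to 0.70 points (0.04 to 0.70 of a standard error). The anti-conservative error rate runs from about 0.028 to 0.104. A middle case (5%, RR 1.5, 5 points) gives a bias of 0.12 points and an error rate of 0.035.

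**The case against.** The strongest reply is that a reader might infer that a measured risk factor has been left unadjusted and that the primary comparison is confounded. The documents do not support that, for three reasons.

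- Collection is documented for XIENCE 28 USA only. Nothing visible says that XIENCE V USA or XIENCE 28 Global recorded smoking, and a propensity covariate has to exist in both comparison groups. Adding it is therefore cheap only if the control data hold it.
- One of the composite scores may contain smoking, and listed covariates such as age, sex, BMI and prior MI may absorb part of a smoking difference.
- Nothing in the documents shows that smoking predicts 1- to 6-month death/MI in this population, or that it differs between the groups.

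These limits stand, and they rule out any claim of demonstrated bias. They do not dispose of the point. A score built for bleeding would carry smoking at a fixed weight not fitted to group membership, and would not ensure balance on smoking within quintiles.

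The outcome-blinded modelling and FDA review are real safeguards against outcome-driven choices. However, the visible text names no step for adding a variable missing from the list. SAP 2.1 plans baseline summaries, so an imbalance could be seen, but seeing it does not adjust for it. Appendix A, cited in SAP 2.9, is not visible and may hold further modelling detail.

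Family history of CAD and race are also recorded in Protocol 6.1.2 and not listed. The gap is thus not specific to smoking, but that does not explain it.

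**Conclusion.** The point holds as a gap in covariate selection. Smoking status is collected in XIENCE 28 USA, is not a covariate in its own right, and is not adjusted for in any other visible analysis. Any resulting bias could run in either direction.

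Under the assumed 4% event rate, 15% smokers and 10-point imbalance, it would be 0.19 to 0.35 percentage points, about a quarter to a half of the unstratified standard error. Smaller imbalances or relative risks make it minor. The margin is not visible, so the effect on the trial's conclusion cannot be judged. The case for acting rests on the low cost of the change and on the weight that a non-randomized primary comparison places on this list, not on evidence that bias is present.

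**What to change.** Before the propensity results go to the FDA, confirm whether smoking status is recorded in XIENCE 28 USA, XIENCE 28 Global and XIENCE V USA, with definitions that can be aligned.

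- **If it is in all three:** add it (current versus not) to list 2.1.3-1, to the baseline multiple imputation in SAP 2.5, and to a balance table within propensity quintiles, completed before outcomes are analysed.
- **If it is missing from any of them:** do not impute it for a whole group. State the gap in the SAP, say whether either composite score carries smoking, and add a quantitative bias calculation over stated ranges of prevalence difference and relative risk.

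The cost is one covariate added to 29 in a model with about 3,000 subjects (1,600 + 1,400). No new data collection is needed in XIENCE 28 USA. The low cost depends on the variable being available in the other two datasets, above all the control.

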2.1.4 Hypothesis Testing

Primary endpoint analysis for 1-month DAPT

The XIENCE 28 USA study is powered based on primary endpoint of Death/MI between 1-month and 6-month follow-up. Death/MI is defined as the composite endpoint of all death or all myocardial infarction (modified Academic Research Consortium [ARC]). This primary endpoint will be evaluated between pooled 1-month DAPT arm and XIENCE V USA historical control stratified by propensity score quintiles in the primary analysis population.

The stratified Farrington-Manning method will be performed to test non-inferiority (NI) of pooled 1-month DAPT compared to standard DAPT duration from XIENCE V USA historical control.

Major secondary endpoint analysis for 1-month DAPT

If the hypothesis testing for the primary endpoint is successful, the hypothesis testing for the major secondary endpoint of bleeding (BARC type 2-5) from 1- to 6-month follow-up will be performed.

The superiority test for the major secondary endpoint will be performed stratified by propensity score quintiles in the primary analysis population.

2.1.5 Survival Analyses

Survival analysis may be conducted to analyze time-to-event variables. Subjects without events will be censored at their last known event-free time point. Survival curves will be constructed using Kaplan-Meier estimates.

Summary tables for the endpoints will include failure rates (Kaplan-Meier estimates). For the primary analysis report, all available data will be used.

2.2 Endpoint Analyses

2.2.1 Primary Endpoint Analysis

Primary Analysis:

A non-inferiority test will be performed on the primary endpoint between 1-month and 6-month follow up for the primary analysis population of the pooled 1-month DAPT arm and the XIENCE V USA historical control stratified by propensity score quintiles [REDACTED]

To ensure all subjects to be included in this analysis, multiple imputations will be performed in calculating the propensity scores.

Secondary Analysis (as a sensitivity analysis):

In addition to the primary analysis stratified by propensity score quintile, a non-inferiority test will be performed on the primary endpoint stratified by propensity score quartile, with the same methodology as described above.

2.2.2 Major Secondary Endpoint Analysis

The stratified Farrington and Manning method will be used for the stratified superiority test of the major secondary endpoint between 1-month and 6-month follow up for the primary analysis

population of pooled 1-month DAPT arm and XIENCE V USA historical control. The stratification is performed by propensity score quintiles.

To ensure all subjects to be included in this analysis, multiple imputations will be performed in calculating the propensity scores.

2.2.3 Secondary Endpoint Analyses

Other secondary clinical endpoints will be descriptively analyzed for both the primary analysis population and all registered subjects without propensity stratification.

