1.3.1 Selection of Control

The XIENCE V USA historical HBR control is derived based on the following criteria:

Definition of non-complex HBR from XIENCE V USA

- HBR inclusion criteria (any one of the below HBR criteria):
 - Age \geq 75 years
 - History of major bleeding
 - History of stroke
 - Receiving or scheduled to receive chronic anticoagulation therapy
 - Renal insufficiency (creatinine > 2 mg/dl)
 - Anemia (Hb < 11 g/dl or transfusion)
 - Thrombocytopenia (platelet count $< 100.000/\text{mm}^3$)
- Exclusion criteria for non-complex:
 - STEMI
 - LVEF $< 30\%$

- Patients with more than 3 lesions treated during index procedure
- Patients with more than 2 vessels treated during index procedure
- At least one lesion with RVD < 2.25 mm or > 4.25 mm (visual estimation)
- At least one lesion located in left main
- At least one lesion located in graft
- At least one CTO lesion
- At least one in-stent restenosis lesion
- At least one target lesion with length > 32 mm by visual estimation.

The above selection criteria for the XIENCE V USA historical control aligns with the key inclusion/exclusion criteria of the XIENCE 28 USA Study.

For primary analysis, the XIENCE V USA non-complex HBR control subjects must be also 1-month clear, following the same logic as defined for the primary analysis population (refer to Section 1.4).

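### Any comparison of the other secondary endpoints with XIENCE V USA would be crude, beside propensity-stratified death/MI and BARC 2-5 results (minor; cheap to improve)

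*SAP*

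**What the plan says.** - **Rule for the other secondary endpoints (SAP 2.2.3).** "Other secondary clinical endpoints will be descriptively analyzed for both the primary analysis population and all registered subjects without propensity stratification". No comparator is named. Protocol 9.4.3 says only that these endpoints are described.
- **What the rule covers (SAP 1.3.3.2).** Death and its components, MI, stroke, stent thrombosis, revascularisation, TLF, TVF and BARC 3-5 at 1-6 months. The section adds that all endpoints, including the primary and major secondary ones, "will also be assessed from 6 months to 12 months and from 1 month to 12 months". It also lists the 1-6 month death/MI composite, which SAP 1.3.2 makes the primary endpoint.
- **Where stratification applies (SAP 2.1.3).** The reason given is that the groups are "not randomized and thus may not have balanced baseline characteristics"; accordingly "the non-inferiority and superiority tests for 1-6 month period will be carried out through stratified analysis". SAP 2.2.1 and 2.2.2 carry this out with propensity score quintiles. SAP 2.3 keeps the quintiles for subgroup comparisons that are themselves descriptive.
- **Other adjustment (SAP 2.7).** None unless specified, and none is visibly specified for these endpoints.
- **Output allowed.** SAP 2.1.2, which gives TLF as an example variable, says: "Differences between two comparison groups of interest, when specified, will be summarized with the difference in percentages". It also permits relative risks and hypothesis-generating p-values. Protocol 9.4 permits p-values for TLR and TVR and has log-rank results displayed. SAP 2.1.5 makes survival analysis optional but puts Kaplan-Meier failure rates in the summary tables.

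**The concern.** The SAP accepts that a non-randomised comparison with a historical control needs adjustment, and applies it to two endpoints in one window. Readers will set all death and all MI beside the stratified death/MI composite, BARC 3-5 beside the stratified BARC 2-5 that contains it, and the 12-month results beside the 6-month ones. If the first of each pair is a crude contrast with XIENCE V USA, a difference in case mix can look like a difference in effect. A component could then appear to contradict, or to reinforce, the adjusted result only because the method changed. What is at stake is interpretation of the supporting evidence, not the confirmatory tests.

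**Working it through.** **No plan figure is at stake.** The margin, assumed rates and power are redacted. The group sizes below are the approximate ones in SAP 1.5: 1,600 test and 1,400 control. The 1,600 equals the US maximum of 800 plus the planned 800 from the Global study; with the US minimum of 640 the sum would be 1,440. Every event rate, imbalance and risk gradient below is an assumption, because the documents give no baseline comparison.

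**Step 1: a worked case with no true effect.** Take five quintiles of 3,000/5 = 600 subjects. The test-arm share runs from 20 points below to 20 points above 53.3%. Risk doubles geometrically from quintile 1 to 5, and the mean rate is 4%.

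| Quintile | Test n | Control n | Risk, both arms | Test events | Control events |
|---|---|---|---|---|---|
| 1 | 200 | 400 | 2.75% | 5.49 | 10.98 |
| 2 | 260 | 340 | 3.26% | 8.49 | 11.10 |
| 3 | 320 | 280 | 3.88% | 12.42 | 10.87 |
| 4 | 380 | 220 | 4.62% | 17.54 | 10.16 |
| 5 | 440 | 160 | 5.49% | 24.16 | 8.78 |
| Sum | 1,600 | 1,400 | | 68.1 | 51.9 |

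- Crude rates: 68.1/1,600 = 4.26% and 51.9/1,400 = 3.71%. The difference is 0.55 points and the relative risk 1.15.
- Standard error: √(0.0426×0.9574/1,600 + 0.0371×0.9629/1,400) = 0.71 points, so difference/SE = 0.77.
- Probability that the crude 95% interval excludes zero: 1 − Φ(1.96 − 0.77) + Φ(−1.96 − 0.77) = 12.0%, against a nominal 5%.
- The quintile-stratified difference is zero by construction.

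With shares varying by ±10 to ±30 points, a risk ratio of 1.5 to 3 between quintiles 5 and 1, and rates of 2% to 8%, the crude difference runs from 0.08 to 2.57 points, and the interval excludes zero in 5.3% to 74% of trials.

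**Step 2: simulation with a continuous score, no true effect.** One normal score, outcome log-odds 0.2 to 0.6 per SD, and a mean shift between arms. The crude test is chi-square or Fisher by the SAP 2.1.2 rule. The stratified test is Mantel-Haenszel over pooled quintiles.

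| Assumed rate | Shift 0.1-0.15 SD: spurious difference; crude p<0.05 | Shift 0.25-0.5 SD: spurious difference; crude p<0.05 |
|---|---|---|
| 0.5% | 0.01-0.05 points; 4-6% | 0.03-0.17 points; 5-9% |
| 1% | 0.02-0.09 points; 5% | 0.05-0.34 points; 5-13% |
| 3% | 0.06-0.27 points; 5-7% | 0.15-0.99 points; 6-31% |
| 6% | 0.11-0.52 points; 5-9% | 0.29-1.9 points; 6-54% |

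- Stratified false positives are 4-6% throughout.
- At 0.5-3% rates the crude relative risk is 1.02-1.09 for small shifts and 1.05-1.35 for larger ones.
- The 31% and 54% each need the largest shift and the steepest slope together.
- If the 1-month DAPT arm is the lower-risk one (3% rate, shift 0.15-0.5 SD), the crude relative risk is 0.75-0.94 and false positives are 6-27%.

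**Step 3: limits of stratification.** With an added unmeasured confounder (0.25 SD shift, log-odds 0.4, 3% rate), stratifying cuts the spurious difference from 0.63-0.99 to 0.35-0.39 points and leaves 8% false positives.

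**Step 4: precision.** In the simulation, stratifying widened the standard error by 0-3%. It costs more when the arms overlap less. In Step 1 the Mantel-Haenszel weights (test n × control n / 600) sum to 686.7, against 1,600×1,400/3,000 = 746.7 unstratified, so the standard error rises by about √(746.7/686.7) − 1 = 4%. For ±30 points the weights sum to 611.7 and the same approximation gives about 10%.

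**The case against.** The strongest reply is that the SAP promises no such contrast. SAP 2.2.3 names no control, and SAP 2.1.2 gives differences only when specified. SAP 1.3.1 says "For primary analysis, the XIENCE V USA non-complex HBR control subjects must be also 1-month clear", and the SAP defines no control counterpart to all registered subjects. Single-arm summaries are a fair reading and carry no confounding. The choice is also disclosed, descriptive, and labelled hypothesis-generating where p-values appear. Table mock-ups and redacted text, which cannot be seen, may settle the display.

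Much of this stands, and several stronger readings that a reader might draw fail:

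- *That the SAP prescribes crude comparisons with XIENCE V USA.* It does not; it only leaves room for them.
- *That SAP 2.2.3 is unusual in naming no comparator.* In SAP 2.9 only the XIENCE 90 comparison names one; the compliance and missing-outcome analyses do not. Nor does the COVID-19 subgroup in SAP 2.3.3 mention the control.
- *That listing death/MI again in SAP 1.3.3.2 creates conflicting primary analyses.* SAP 2.2.1 governs the primary endpoint. An extra unstratified rate does no harm unless it is contrasted with the control.
- *That error control is weakened.* These endpoints are outside the sequential tests.

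What the reply does not remove is that ruling out propensity stratification means little for single-arm rates, and that the permitted two-group statistics and log-rank output need a second group. Nor is being descriptive a full answer, since SAP 2.3 keeps the quintiles for descriptive subgroup comparisons because baseline characteristics should be comparable within them. One could also attach the exclusion of stratification to the all-registered set alone. The sentence reads less naturally that way, and that reading would itself need stating.

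**Conclusion.** The point holds as a minor one. If the other secondary endpoints, or any endpoint in the later windows, are contrasted with XIENCE V USA, the visible plan makes that contrast unadjusted, for a reason the SAP does not give and against its own reasoning in 2.1.3 and 2.3. This is conditional on a contrast being shown. It does not touch alpha, the primary claim or the major secondary claim.

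Neither the size nor the direction of the bias can be known from the documents. It is negligible when imbalance is small or events are rare, and grows with commoner events and longer windows. Restricting the control by similar selection criteria (SAP 1.3.1) narrows the imbalance but does not adjust for what remains. The figures above show what is possible under stated assumptions; they are not estimates for this trial. Redacted text could add detail, but to remove the point it would have to override the visible sentence in SAP 2.2.3.

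**What to change.** Amend SAP 2.2.3 along these lines:

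1. **More frequent endpoints, 1-month clear population.** Any contrast with XIENCE V USA for all death, all MI, BARC 3-5, TLF and TVF, and for death/MI and BARC 2-5 in the later windows, is a risk difference with 95% CI. It is stratified by the existing propensity score quintiles and combined across the imputations.
2. **Later windows.** State the risk set; for 6-12 months, subjects still in follow-up at 6 months. Use quintile-stratified Kaplan-Meier differences where censoring matters, and stratify any log-rank test by quintile.
3. **Rarer endpoints and all registered subjects.** Show results by arm, labelled unadjusted, without between-group p-values. At a 0.5% rate there would be about 8 against 7 events and a half-width of 1.96×√(0.005×0.995×(1/1,600 + 1/1,400)) = 0.5 points, so adjustment would add little.
4. **Death/MI at 1-6 months.** State that the entry in SAP 1.3.3.2 is the primary endpoint and is compared with the control only as in SAP 2.2.1. Nothing need be deleted, so the list stays aligned with Protocol 4.3.
5. **If no control contrast is intended,** say that these endpoints are summarised for the 1-month DAPT arm only.

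Cost: SAP wording and programming, with no new data. Item 1 gives 5×3 + 2×2 = 19 contrasts, or 19×10 = 190 estimates if the 10 imputed datasets of SAP 2.9 are used. Intervals widen slightly (0-3% in the simulation, more with poor score overlap), and only measured confounders are adjusted.
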